The goal of this study is to evaluate the main effect on carcinogenesis related biomarkers, inflammatory biomarkers and magnesium status by reducing the dietary Ca/Mg intake ratio to under 2.6 by magnesium supplementation on carcinogenesis related biomarkers, inflammatory biomarkers and magnesium status and to estimate the potential interaction between magnesium treatment and the Thr1482Ile polymorphism (G→A) of the *TRPM7* gene. The study will enroll 288 participants with colorectal hyperplastic polyp or/and adenoma, polyps free but being at high risk of colorectal polyps or cancer, 152 of whom have the GG genotype and 136 of whom have GA/AA genotype. These participants will be randomized to either treatment or placebo using a double-blind two-factorial (Ca/Mg intake ratio and genotype) design so that each treatment/placebo arm will contain 60 participants with the GG genotype and 60 participants with at least one A allele. Based on the participant's Ca/Mg intake ratio (obtained from the two 24-hour recalls), he or she will be assigned to a dose that will reduce the Ca/Mg intake ratio to around 2.3 (less than 2.6 but no less than 2.0). The dose of magnesium supplementation is personalized based on the current intake ratio. The duration of the study from recruitment through the end of the intervention is approximately 14 weeks including a 12-week intervention. (See attached Figure E2)

The trial will be double-blind: neither participants nor research staff who interacts with the participants or their samples will be aware of the treatment assignments. The treatment period will last for 12 weeks.

Procedures:

1. Intervention layout

- Based on the participant's Ca/Mg intake ratio (obtained from the two 24-hour recalls), the participant will be assigned to a dose that will reduce the Ca/Mg intake ratio to around 2.3 (less than 2.6 but no less than 2.0). Each dose will correspond to one or multiple capsules from three different sizes of magnesium supplementation or placebo.
- Presented in Table E2 is the detailed treatment dosage based on baseline calcium/magnesium ratio and calcium intake level as well as resulting calcium/magnesium ratio after supplementation. Treatment or placebo capsules will be discarded if they are not used within 6-months.

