- Complete the Biological Specimen Transit Log and Laboratory log

--- Clinic Visit #4 (Magnesium Tolerance Test)

Location

Clinic Visit #4 will be in the Clinical Research Center (CRC) at Medical Center North, 3rd floor on the Vanderbilt Campus

Scheduling

Participants will receive a schedule of planned the magnesium tolerance test on two consecutive days. A 24 hour urine sample will be collected for determining the basal urinary magnesium excretion prior to the intravenous infusion of magnesium sulfate. Another 24 hour urine sample will be obtained starting with the IV infusion.

Preparation

Documents

- Reminder Call Script for Clinic Visit #4
- Biological Specimen Collection Form H_4
- Clinic research progress note

Medications for magnesium tolerance test

- Magnesium sulfate, 2 g in 50 ml, 0.325 mEq/mL; Hospira, Inc., Lake Forest, IL
- 500 ml of 5% dextrose

Blood draw supplies (see the Blood Draw Protocol)

Participant packet

- Instruction for 24 hour urine collection
- 24 hour urine collection kit
- Clinic visit questionnaire form
- FedEx label

Procedures:

1. Preparation on the day prior to Clinic Visit #4
 - The PPCCT research staff will place a reminder call (REMINDER CALL SCRIPT for CLINIC VISIT #4, Appendix F) on the day prior to clinic visit #4.
 - A reminder email will be sent to the recruited participant to remind him/her of the time, date of the clinical visit.
 - The PPCCT research staff will prepare all the materials needed for clinic visit #4 on the day prior to the fourth clinic visit.
3. The PPCCT research staff will meet the participant at the Clinical Research Center on the day of Clinic Visit #4
 - Explain the purpose of the magnesium tolerance test with the participant again.
 - Obtain the 24 hour urine sample and temporarily store the samples in the freezer at CRC. Review the clinic visit questionnaire form. Record the information on 24 hour urine collection (pre magnesium tolerance test) in the Biological Specimen Collection Form H_4.

- Blood samples will be obtained prior to the IV. Infusion and the Blood draw protocol will be applied. The collection information will be recorded in the Biological Specimen Collection Form H_4.

4. Magnesium Tolerance Test (MTT)

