- Infuse 0.2mEq (2.4mg) elemental magnesium per kilogram of body weight in 500 ml of 5%dextrose over 4 hours, which will be conducted by the CRC nurses. (The infusion is no faster than 8meq of magnesium sulfate per hour. Participants with a body weight of 160kg or greater are ineligible for the magnesium tolerance test.)
- Collect urine (starting with infusion) for magnesium and creatinine for 24 hours.

5. MTT safety monitoring

- The infusion is no faster than 8meq of magnesium sulfate per hour. Participants with a body weight of 160kg or greater are ineligible for the magnesium tolerance test.
- We will check and record the participant's blood pressure and heart rate before initiating the Magnesium sulfate intravenous drip infusion and monitor and record the same in the course of a four-hour infusion and within 1 hour following the infusion completion.
- In addition, the participant's hemoglobin oxygen saturation levels (%), blood pressure, heart rate and respiration rate will be monitored continuously throughout the time of admission by experienced registered nurses at the CRC.
- An attending physician, who is knowledgeable about the study and is part of the study team (a co-investigator), will be on call to accompany each participant during the Magnesium Tolerance Test.
- In the event of a life-threatening situation, the participant will be sent to emergency room or a life-support team will be called to the CRC.

6. Percentage magnesium retained is calculated by the formula below

$$\left[1 - \frac{(\text{post infusion Mg excretion} - \text{basal Mg excretion}^*)}{\text{total Mg infused}} \right] \times 100$$

$$* \text{basal Mg excretion} = \frac{\text{pre - infusion urine Mg}}{\text{pre - infusion urine Creatinine}} \times \frac{\text{post - infusion 24hour urine}}{\text{Creatinine}}$$

7. Criteria for magnesium deficiency

- $\geq 50\%$ retention at 24 h: definite deficiency
- 25% to $< 50\%$ retention at 24 h: probable deficiency
- $\leq 25\%$ retention at 24 h: normal

8. A letter will be mailed to the participant to inform them of his/her body magnesium status (Appendix K).

--- Clinic Visit #5 --- (Post Magnesium Tolerance Test)

Location

Clinic Visit #5 will be in the Clinical Research Center (CRC) at Medical Center North, 3rd floor on the Vanderbilt Campus

Scheduling

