Urinary creatinine levels will be determined spectrophotometrically using a kit from Sigma Chemical Co. (St. Louis, MO) as performed previously. This assay requires 0.01 ml of urine sample for each subject and uses a test kit from Sigma Company (Sigma, St. Louis, MO). The assay is based on a modification of the Jaffe reaction by measuring the color intensity difference of a creatinine picrate complex before and after acidification. In our previous studies, the mean CVs for intra- and inter-assay variability were found to be 4.1 % and 6.7%, respectively.

Urinary Heavy Metal Measurement

Urinary heavy metal concentration will be determined using [Inductively Coupled Plasma Mass Spectrometry \(ICP-MS\)](#) at the Vanderbilt Mass Spectrometry Core laboratory.

Urinary Magnesium Measurement

Urinary magnesium concentration will be determined at the Vanderbilt University Hospital laboratory.

Urinary eicosanoids metabolites measurement

Assay of eicosanoids metabolites in biospecimen will be performed.

24 Hour Urine Collection for Magnesium Tolerance Test

Magnesium load test is a reliable indicator of magnesium status and considered as the gold standard for the diagnosis of magnesium deficiency. This test requires a pre-test 24 hour urinary magnesium content, followed by a second 24 hour urinary magnesium content, after initiating the intravenous magnesium sulfate infusion. Performing this test need well trained staff. It is not a method that can be used as a routine test for the evaluation of Mg status.

Location

Clinical Research Center (CRC) Medical Center North, 3rd floor on the Vanderbilt Campus

Scheduling

Participants will receive a schedule of planned the magnesium load test on a two consecutive days. A 24 hour urine sample will be collected for determining the basal urinary magnesium excretion. Another 24 hour urine sample will be obtained following the load test.

Preparation

Sterile specimen containers with ascorbic acid
10-1.8ml cryovials vials
Specimen box
Labels
Permanent markers
Biohazard Bags

Procedure

1. Collect 24 hour urine the day before the load test for basal magnesium and creatinine ratio.
2. Infuse 0.2mEq (2.4mg) elemental magnesium per kilogram of body weight in 50 ml of 5%detrose over 4 hours, which will be conducted by CRC nurses.
3. Collect urine (starting with infusion) for magnesium and creatinine for 24 hours

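### The tolerance-test infusion is written with two volumes, one Table E2 entry lists a dose that misses the target ratio, and the under-2.6 target is stated without its exceptions

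*Combined protocol and SAP*

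**What the plan says.** **Infusion.** Section 6.0, 24 Hour Urine Collection for Magnesium Tolerance Test, has nurses give the 0.2 mEq/kg load as "elemental magnesium per kilogram of body weight in 50 ml of 5%detrose over 4 hours". In section 6.0 F, Clinic Visit #4, the medication list has "500 ml of 5% dextrose" and the procedure reads "elemental magnesium per kilogram of body weight in 500 ml of 5%dextrose over 4 hours". That visit also names the stock, "Magnesium sulfate, 2 g in 50 ml, 0.325 mEq/mL", and sets two limits: "The infusion is no faster than 8meq of magnesium sulfate per hour" and "Participants with a body weight of 160kg or greater are ineligible for the magnesium tolerance test". The urine section repeats neither limit.

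**Oral dose.** In section 6.0 E, Intervention Protocol, each participant is to be "assigned to a dose that will reduce the Ca/Mg intake ratio to around 2.3 (less than 2.6 but no less than 2.0". The next bullet makes the table the dosing instrument: "Presented in Table E2 is the detailed treatment dosage based on baseline calcium/magnesium ratio and calcium intake level". In Table E2, the cell for band 3.6-3.8 at calcium 1800 lists two blue capsules and a resulting ratio of 2.51.

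**Dose limits.** Sections 1.0 and 7.0 state ceilings relative to the DRI (40 mg and 100 mg/day above it). Neither is tied to the ratio target. The largest regimen in Table E2 and in the dose reduction table is one blue and three orange capsules, 389.55 mg.

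**The concern.** Pharmacy procedures are built from a table supplied by the PI, so a wrong capsule count can become a wrong dispensed dose. If the count is the faulty part of the 3.6-3.8/1800 cell, a participant dosed as printed gets 77.25 mg/day less than intended. That participant also stays above the ratio that Aim 1 sets out to reach. Calcium 1800 is within the eligible range (700 to under 2000 mg/day).

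The infusion conflict concerns a second written copy of one intravenous step, and staff should not have to choose between two volumes.

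The unqualified target matters for interpretation. Aim 1 evaluates reducing the ratio to under 2.6, yet for some eligible intake patterns the table itself shows that the maximum dose does not do so.

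**Working it through.** **Inputs.** Elemental magnesium per capsule (Intervention Protocol and dose reduction table): blue 77.25 mg, orange 104.10 mg, green 73.35 mg. Table E2 has 25 bands and 14 calcium columns, so 350 cells.

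**Table formula.** Resulting ratio = Ca / (Ca / mid-band ratio + supplemental Mg). This reproduces 339 of the 350 printed ratios within 0.0092, including the other 13 cells of band 3.6-3.8. For example, 3.6-3.8 at 1900 with three blue capsules gives 1900/(1900/3.7 + 231.75) = 2.549, printed 2.55.

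**The off-target cell, 3.6-3.8 at 1800.**
- Two blue: 1800/(486.49 + 154.5) = 2.81; at the band edges 2.75 and 2.87. No point in the band is below 2.6.
- Three blue: 1800/(486.49 + 231.75) = 2.506, the printed 2.51; at the edges 2.46 and 2.55.
- Sequence at calcium 1800: 208.2 mg in band 3.4-3.6, 154.5 mg here, 285.45 mg in band 3.8-4.0. The only other fall in that column is from 104.1 to 77.25 mg between bands 2.6-2.8 and 2.8-3.0, where printed and computed ratios agree.

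**The ten other mismatches.**

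| Band / Ca | Printed | Computed | Pattern |
|---|---|---|---|
| 3.4-3.6 / 1000 | 2.22 | 2.31 | capsules and ratio of preceding band |
| 3.4-3.6 / 1100 | 2.29 | 2.39 | same |
| 3.4-3.6 / 1300 | 2.26 | 2.35 | same |
| 3.4-3.6 / 1700 | 2.30 | 2.40 | same |
| 5.2-5.4 / 700 | 2.20 | 2.23 | same |
| 3.8-4.0 / 1100 | 2.24 | 2.37 | fits two orange (2.24) |
| 6.8-7.0 / 800 | 2.14 | 2.30 | fits two blue + one orange (2.14) |
| 6.8-7.0 / 900 | 2.16 | 2.31 | fits one blue + two orange (2.16) |
| 3.4-3.6 / 1200 | 2.22 | 2.29 | neither |
| 3.4-3.6 / 1500 | 2.23 | 2.30 | neither |

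The differences run from 0.03 to 0.16. Across their bands these ten cells give 2.215 to 2.442, inside the target. In all 11 mismatching cells the printed value lies outside the range obtainable anywhere in the band.

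**Maximum-dose cells.** Dropping the calcium-2000 column leaves 25 × 13 = 325 cells. Of these, 27 print 2.6 or more, up to 2.96 (7.4-7.6 at 1900), all at 389.55 mg and all correct at mid-band. Twelve print 2.70 or less. At the lower band edge two fall just under 2.6:
- 6.4-6.6 at 1700: 1700/(1700/6.4 + 389.55) = 2.595
- 7.0-7.2 at 1600: 1600/(1600/7.0 + 389.55) = 2.588

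The other 25 stay at or above 2.6 throughout. Conversely, four cells printed at 2.58 or 2.59 pass 2.6 at the upper edge: 2.8-3.0/1800 (2.66), 4.4-4.6/1900 (2.62), 5.4-5.6/1900 (2.61) and 5.8-6.0/1800 (2.61).

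**Infusion.** Stock volume needed: V = 0.2 × kg / 0.325 ml. At 70 kg the dose is 14 mEq and V = 43.1 ml.
- Volume read as diluent: 14/(500 + 43.1) = 0.026 mEq/mL against 14/(50 + 43.1) = 0.150 mEq/mL, a 5.8-fold difference. Over an assumed 50 to 120 kg it runs from 6.6-fold down to 4.6-fold.
- Volume read as final volume: a 10-fold difference, but 50 ml of stock holds only 50 × 0.325 = 16.25 mEq, enough for 16.25/0.2 = 81.25 kg. Above that weight a 50 ml final volume cannot be made from this stock, while the protocol excludes only 160 kg or more.
- Hourly rate: 0.2 × kg / 4, whichever volume is used; 8 mEq/h is reached at 160 kg.

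**The case against.** The infusion conflict looks like a one-digit slip. Two entries for the visit itself say 500 ml, and 50 ml is the volume of the magnesium sulfate stock, which may be its source. Dose, rate cap and retention formula are untouched. That is fair, and no harm is claimed.

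The off-target cell turns on one digit in a table whose extracted text is imperfect: the footnote below it prints the green capsule twice, as 73.35 and 75.55 mg. A reading error from the PDF cannot be excluded. The printed 2.51 also points to its own correction, any error is toward less magnesium, and a physician signs each prescription and may catch it. These points justify checking the source before changing anything. They do not remove the contradiction in the text as it stands, and nothing in the plan shows that the signature step would catch it.

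The cells above 2.6 are printed openly, and the target bullet is followed directly by a pointer to the table, so the third part is a missing qualifier rather than a hidden failure. That stands. The ten further mismatches do not breach the target; they matter mainly as a sign that the table was not fully checked. No endpoint formula or power figure is involved.

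**Conclusion.** The concern holds. One of 350 Table E2 cells lists a dose that contradicts its printed result and misses the target: 2.81 against 2.51. Two written volumes for the same infusion conflict, 50 ml against 500 ml, and the urine-section figure is the likely slip. The under-2.6 statement has 27 printed exceptions among the 325 cells with calcium below 2000; this part is a wording point. The table entry carries the most weight, then the volume.

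The result assumes the extracted table matches the source, the green capsule is 73.35 mg, and each calcium column is taken at its printed value. The counts are shares of cells, not of people. The colour coding that restricts some rows to men is not visible in the text, so the cells cannot be tied to who could receive those doses. The number of participants affected, and any effect on Aim 1, is unknown.

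**What to change.** 1. Have the investigator and the pharmacy confirm one infusion volume and correct the other place.
2. Check the 3.6-3.8/1800 cell against the source table and correct it before it is used for dispensing. Then check the capsule entry in the three cells that fit a larger regimen (3.8-4.0/1100, 6.8-7.0/800 and 900) and the printed ratio in the other seven.
3. Qualify the target in the Intervention Protocol, for instance as below 2.6 up to the maximum dose, rather than raise doses. Report the achieved Ca/Mg ratio by arm; the four on-treatment recalls already supply much of the data.

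No dose or volume is proposed here. The cost is one corrected volume, one corrected cell, ten checked cells, one phrase, a short amendment and a pharmacy notice.

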 - The study design, magnesium supplementation, the biospecimen and data collection in this study will be described.
 - Participants will be invited to make three clinic visits at the Clinic Research Center, Vanderbilt University during the period of 12-week intervention and two additional clinic visits for the magnesium tolerance test after completion of the 12-week intervention.
 - Compensation
 - \$250 for all clinic visits
 - Additional \$50 for consistently providing fasting blood sample during the study
 - Magnesium supplementation trial
 - Magnesium/placebo pills orally taken with breakfast meal daily for 12 weeks
 - Magnesium supplementation safety and compliance will be closely monitored and carefully taken care of via phone calls, pill count report, serum magnesium measurement, and renal function test, etc.
 - Participants will be asked to provide the following biological samples at week 0, week 6 and week 12 during the study respectively.
 - Rectal biopsies × 2 (obtained at week 0 and week 12)
 - Blood samples × 3 (collected on biopsy days and at week 6)
 - Urine samples × 3 (collected on biopsy days and at week 6)
 - Stool samples × 3 (collected on biopsy days and week 6)
 - Saliva samples × 3 (collected on biopsy days and week 6)
 - Nail samples × 2 (collected on biopsy days)
 - Hair samples × 2 (collected on biopsy days)

- Skin swab samples × 3 (collected on biopsy days and week 6)
- Participants who undergo magnesium tolerance test will be asked to provide the following samples prior to the test and following the initiation of magnesium tolerance test.
 - 24 hour urine samples × 2
 - Fasting blood samples × 2
- We will measure the body size and vital signs for the participants during each clinic visit.
 - Weight
 - Height
 - Waist-hip circumference
 - Blood pressure
- The risks and benefits of the study will be discussed.
- The participant will be told that participation is voluntary.
- Review the inclusion and exclusion criteria again.
- Answer participant's questions and concerns.
- Further evaluate the participant's interest.
- Obtain the signed Informed Consent Form and give a copy of signed consent to the participant
- Obtain the signed Payment Authorization Form

3. After obtaining the signed consent form, the PPCCT research staff will perform the following procedures with the help of the CRC nurse

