We will test the carcinogenesis-related biomarkers and use the vitro system to identify the most effective and optimized agents. (1) cell biological features: epithelial and stromal morphology; (2) immunophenotypes: CK5/14; CK8/18; Pan-CK; Vimentin; Smooth muscle actin detected by IF staining; (3) molecular signaling pathways; (4) organ-specific gene expression (5) carcinogenesis-related biomarkers; (6) stemness.

Measurement of Microbiomial Markers

Micorbiomial markers in rectal biopsy/swab samples will be measured at baseline, 3-month after the magnesium supplementation.

Measurement of other IHC biomarkers

IHC markers (e.g. CES1, CES2, DEC1, pMLKL) in rectal biopsy samples will be measured at baseline, 3-month after the magnesium supplementation.

Title of Study: Personalized Prevention of Colorectal Cancer Trial

IRB#:

Study Note

Date: Time:

Anoscopy with Rectal Biopsy for Study Protocol

Patient's Name:

Operator: [name]

Procedure: Anoscope was gently inserted into the anus. The obturator was then removed. Using a flexible biopsy forceps - model DBF-2.4-160-S (Cook Medical Inc.) , 8 specimens were obtained. Blood loss was minimal. The anoscope was removed. No complications noted. Patient was monitored per study protocol.

[name]

Title of Study: Personalized Prevention of Colorectal Cancer Trial

IRB#:

Study Note

Date: _____ Time: _____

Anoscopy with Rectal Biopsy for Study Protocol

Patient's Name:

Operator: [name]

Procedure: Anoscope was gently inserted into the anus. The obturator was then removed. Using a flexible biopsy forceps - model DBF-2.4-160-S (Cook Medical Inc.), 8 specimens were obtained. Blood loss was minimal. The anoscope was removed. No complications noted. Patient was monitored per study protocol.

[name]

--- Blood Sample Collection

Blood Draw Protocol

In the study, erythrocyte magnesium (a candidate biomarker for marginal magnesium deficiency) will be used as the primary endpoint to monitor magnesium status and the compliance of treatment, complimented by the secondary endpoint, serum magnesium. Blood samples will be collected at weeks 0, 6 and 12 during the course of magnesium treatment.

In the study, serum magnesium, vitamin D and plasma C-reactive protein will be measured as secondary endpoints to evaluate the effects of the reduction of dietary Ca/Mg intake ratio by magnesium supplementation.

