Measurement of miRNA profiling

Assay of miRNA in biospecimen will be performed.

Measurement of circulating inflammatory biomarkers

Assay of circulating inflammatory biomarkers (e.g. GGT, HBVs, HCV, TNF and others) in biospecimen will be performed.

--- Urine Sample Collection

Urine Collection and Handling Protocol

The fasting urine samples will be collected prior to the treatment (week 0), the midpoint (week 6) and the end of intervention (week 12). Each urine sample will be collected in a sterile urine specimen container containing 100 mg ascorbic acid as a preservative.

Location

Clinical Research Center (CRC) Medical Center North, 3rd floor on the Vanderbilt Campus

Scheduling

Participants will receive a schedule of planned fasting urine collections. A urine sample will be collected on the biopsy collection day at the beginning and the end of the intervention phase respectively, at week 0 and week 12. An additional urine sample will be collected at the midpoint of the intervention phase, at week 6. All samples on a given participant will be taken at the same time of day to avoid potential variability due to circadian rhythm.

Preparation

Sterile specimen container 20 ml with 100 mg ascorbic acid

10-1.8ml cryovials vials

Specimen box

Labels

Permanent markers

Biohazard Bags

Procedure

Before the clinic visit, participants will be mailed:

- Sterile urine containers containing a preservative
- Zip-lock bags/ biohazard bags
- Insulated bag with ice packs
- Patients will be given written and verbal instructions for collection of urine samples
- Patients will be instructed to:
 1. Collect the fasting urine of the day.
 2. Place specimen in zip-lock bag / biohazard bag.
 3. Fill the urine collection questionnaire (Appendix G)
 4. Store specimen in the freezer until ready to leave for clinic.
 5. Place zip-locked bag in insulated bag with ice pack.
 6. Transport the sample to the clinic.
 7. Give specimen to study staff and receive clean container for next collection.

Urine Processing

- Urine specimens will be stored in CRC freezer.
- Specimens will be processed within 4-6 hours after collection.
- All specimen's will be labeled with date, participant ID #.
- 1-2 ml aliquots of the urine sample will be pipetted into each of 9-labeled cryovials.
- Vials will be placed in specimen box for storage.
- Remaining specimen will be discarded.
- Study staff will then transport specimens to [name] [name], [name].

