Because we wish to reduce participant burden, we will not conduct a placebo run-in period to assess participant compliance. We will also not conduct a run-in period for tolerance to magnesium supplementation because magnesium is a dietary supplement which has been well tolerated in previous studies with a low rate of reported adverse events. The dose of magnesium supplementation is personalized based on the current intake ratio, thus, the dose used in the proposed trial is generally smaller than that used in most previous studies, and provides additional assurance for the safety of participants. Thus, we predict the drop-out rate will be low based on previous clinical trials and our experience.

In the study, the research nurses or the research staff will telephone each participant for any adverse events as well as compliance monitoring. Furthermore, changes in serum and erythrocyte magnesium (baseline, the middle and the end of the study) will also be used to monitor compliance. We will follow the Vanderbilt Data Safety Monitoring (DSM) Plan

Procedures

- The day following each of the in-person visits (baseline, week 6, and week 12), the research staff or nurse will telephone each participant to monitor for any adverse events due to biospecimen collection as well as compliance monitoring.
- During the 12-week intervention, research staff from the SRSR or the research nurse will contact the participants to check their adherence to study treatment and to ask if there are any potential adverse events, 3 times of safety monitoring calls at week 1-6 and 3 times at week 7-12 until the twelfth week of trial has completed.
- Research staff will also check the participant's adherence to study treatment by undertaking pill counts during the in-person visits at week 6 and week 12.
- In addition, we will also assess compliance using 24-hour recalls, two diet recalls conducted at week 1 – 6 and another two at week 7-12, using food-record assisted 48-hour recalls conducted at weeks 5 and 11.

In all, the participant will be followed up by phone or in-person visit 13 times for compliance and safety monitoring during the 12 weeks of intervention.

Data and Safety Monitoring Plan

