Univariate analyses will be conducted for these ten primary and secondary end points (continuous variables) in relationship to magnesium treatment and placebo using between-group t-test or non-parametric tests within genotype groups. The difference in the study endpoints (primary+secondary) between magnesium supplement and placebo will be estimated for the genotype groups (GG, GA, AA and GA and AA combined) along with their 95% confidence intervals. The interaction between the genotype and intervention will be estimated as the difference of the within-genotype magnesium supplement versus placebo differences.

Two-way ANOVA or ANCOVA analyses will be conducted to analyze the primary and secondary endpoints with intervention and genotype in the model (ANOVA) or other potential confounders including polyp type, size, and location for primary hyperplastic polyp or/and adenoma as well as body mass index, age, total energy intake, and intakes of other nutrients (average of six 24-hour recalls) in the model (ANOCOVA). Overall intervention effect and genotype effect and their interactions will be tested.

Administrative Interim analyses Administrative interim analyses may be performed as needed prior to the completion of the clinical trial over the 5 year period. One example of such administrative interim analyses is to generate preliminary data for a new grant submission. The study team does not even have any intention to stop the trial at these interim analyses, thus there is no need to establish a stopping rule. A biostatistician from outside the study team will perform such analyses on unblinded data. All study team members remain blinded until the completion of the study. However, summarized study group-level data from such interim analyses may be communicated to the study PI's solely for the purpose of planning other studies.

Routine data monitoring will be conducted to ensure data quality. All the statistical analyses will be conducted by or under the guidance of [name], one PI of the study.

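### The planned models for the blood and urine endpoints have no visit term and no baseline value of the endpoint, which costs efficiency, mostly through the missing baseline covariate

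*Combined protocol and SAP*

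**What the plan says.** **Sampling.** The Blood Draw Protocol (section 6.0, part F) states: "Blood samples will be collected at weeks 0, 6 and 12 during the course of magnesium treatment". The Urine Collection and Handling Protocol gives the same three times: "The fasting urine samples will be collected prior to the treatment (week 0), the midpoint (week 6) and the end of intervention (week 12"). Tissue is different. The clinic visit #1 procedures list "Rectal biopsies × 2 (obtained at week 0 and week 12"), so the mucosal endpoints have no mid-study value. The magnesium tolerance test is done once, after treatment.

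**Analysis.** Section 6.0, part I, repeated in section 9.0, names t-tests or non-parametric tests between arms within genotype groups. It then says: "Two-way ANOVA or ANCOVA analyses will be conducted to analyze the primary and secondary endpoints" "with intervention and genotype in the model (ANOVA"), or with a list of polyp, body-size, age and dietary covariates added (ANCOVA). "Overall intervention effect and genotype effect and their interactions will be tested". The list contains no visit term, no subject term and no week 0 value of the endpoint. The only averaging mentioned is of the dietary recalls.

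**Role of the mid-study results.** Part G uses "changes in serum and erythrocyte magnesium (baseline, the middle and the end of the study") to monitor compliance. The Blood Draw Protocol gives erythrocyte magnesium the role of tracking magnesium status and compliance. No week 6 role in the treatment comparison is stated for C-reactive protein (CRP), vitamin D or the prostaglandin metabolite (PGE-M).

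**The concern.** A t-test or a two-way ANOVA of this form takes one value per participant. Each participant who completes the study supplies three blood and three urine samples, and the models as written make no provision for two of the three. Two things follow:

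- The week 0 value, usually the strongest predictor of the week 12 value of the same marker, is not used to reduce residual variance.
- If the analysed value is the week 12 value, a participant with a week 6 but no week 12 sample contributes nothing. The analysis sections say nothing about missing data.

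The endpoints affected are serum magnesium, vitamin D, CRP and PGE-M, all secondary in the analysis plan, and erythrocyte magnesium. Erythrocyte magnesium is absent from the endpoint lists in Aim 1 and the analysis plan, but section 9.0 calls it a primary endpoint and bases the power calculation on it. At the standard deviation (SD) that section 9.0 calls conservative, the stated power is 71%, so efficiency on this marker matters.

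**Working it through.** **1. Reproduce the plan's own power.** Inputs from section 9.0: 60 participants in each of 4 cells; placebo means 5.25 (GG) and 4.49 (GA/AA) mg/dL; treated means 5.25 in both; SD 0.830 or 1.16; two-sided 5%.

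- Main effect: 5.25 − (5.25 + 4.49)/2 = 0.38.
- Interaction contrast: (5.25 − 4.49) − (5.25 − 5.25) = 0.76.
- Noncentral F with 1 and 236 degrees of freedom: 94.2% at SD 0.830 and 71.5% at SD 1.16, the same for main effect and interaction.

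The stated figures are 94% and 71%. They reproduce with 240 independent values, one per participant and no baseline adjustment. That supports the single-value reading of the models.

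**2. Assumption for what follows.** The documents give no within-person correlation. I assume the same correlation r between any two of weeks 0, 6 and 12, with r from 0.5 to 0.8, and equal variances.

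**3. Variance of the treatment contrast, relative to unadjusted week 12.**

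| Analysis | Formula | r = 0.5 | r = 0.8 |
|---|---|---|---|
| Week 12, no baseline | 1 | 1 | 1 |
| Week 12, week 0 covariate | 1 − r² | 0.75 | 0.36 |
| Mean of weeks 6 and 12, no baseline | (1 + r)/2 | 0.75 | 0.90 |
| Mean of weeks 6 and 12, week 0 covariate | (1 + r)/2 − r² | 0.50 | 0.26 |

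- The baseline covariate alone cuts the week 12 variance by 25% to 64%. At SD 1.16, power goes from 71.5% to 83.1% (r = 0.5) or 98.8% (r = 0.8).
- Averaging weeks 6 and 12 without baseline cuts variance by 10% to 25%.
- With baseline, the average compared with week 12 gives 0.50/0.75 = 0.667 and 0.26/0.36 = 0.722, a cut of 28% to 33%.

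**4. When the average stops helping.** Let k be the week 6 effect as a fraction of the week 12 effect. The average carries (1 + k)/2 of the week 12 effect, so it is better only if k > 2√(variance ratio) − 1.

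- No baseline: 2√0.75 − 1 = 0.73; 2√0.90 − 1 = 0.90.
- With baseline: 2√0.667 − 1 = 0.63; 2√0.722 − 1 = 0.70.

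**5. What week 6 adds to the week 12 contrast.** With complete data and an unstructured model, nothing. With missing week 12 values, take the extreme case: 288 enrolled, all with weeks 0 and 6, and 288 − 240 = 48 without week 12. Given week 0, the correlation between weeks 6 and 12 is r/(1 + r), which is 0.333 or 0.444; its square is 0.111 or 0.198. Since 48/288 = 1/6,

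effective n = 240 / [1 − (r/(1 + r))² × 1/6].

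- r = 0.5: 240/(1 − 0.0185) = 244.5, a gain of 4.5.
- r = 0.8: 240/(1 − 0.0329) = 248.2, a gain of about 8.

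That is roughly 2% to 3% of 240.

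**The case against.** The case for leaving the plan alone has several parts.

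- **The test is valid.** An end-of-treatment comparison in a 12-week randomised trial is conventional, and a single-value ANOVA creates neither bias nor type I error inflation in itself. This stands.
- **The single-value reading is inferred.** The plan never says whether the analysed value is week 12, a change or an average. This also stands. The model terms and the reproduced power figures make one value per person the natural reading, but the form of that value is left open.
- **Week 6 has a purpose.** It monitors magnesium status and compliance, and the visit also covers pill counts and re-dispensing. A reader might infer that the samples are wasted; the documents do not support that.
- **Week 6 values may not exist for every marker.** No assay times are given for CRP, vitamin D or PGE-M, and remaining aliquots are stored. It cannot be said that measured week 6 results on these markers are discarded.
- **The gain is easy to overstate.** A reader might attach the 10% to 33% variance cut to the week 12 estimate, but it belongs to the week 6/12 average. A reader might also take 48 × r², or 12 to 31 recovered participants. That ignores the baseline covariate, which already carries much of the same information. Nor do the documents say that all 48 extra enrollees are lost after week 6. Some may be excluded on renal function or a pregnancy test after visit #1, and part G predicts low drop-out.

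What survives is the absent baseline covariate and the unused mid-study magnesium values, both already planned for measurement. Some participants may give fasting samples in place of the visit #1 and #3 draws only, so week 6 may differ in fasting state. That argues for week 12 as the main estimate.

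**Conclusion.** The point holds as one of efficiency and missing-data handling. The models for the blood and urine endpoints have no visit term and do not adjust for the endpoint's own week 0 value. The mucosal endpoints have no week 6 value and fall outside the repeated-measures part.

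Most of the available gain for a week 12 estimate comes from the baseline covariate. The contribution of week 6 to that estimate is small: nothing with complete data, and only a few effective participants even in the extreme loss pattern. The week 6/12 average is more precise, but it answers a different question and helps only if most of the effect is present by week 6. The sizes rest on the assumed equal correlation of 0.5 to 0.8; the recovery figure also assumes that loss after week 6 is explained by the values already observed.

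A reader might infer that the planned tests are invalid or that the trial's main conclusions are at risk. Neither follows from the documents.

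**What to change.** In section 6.0, part I, and section 9.0:

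- **Serum and erythrocyte magnesium.** Replace the single-value ANOVA with a mixed model for repeated measures: weeks 6 and 12 as outcomes, week 0 as covariate, arm, genotype, visit and their interactions, and unstructured covariance. Make the week 12 contrast the main estimate and the week 6/12 average supportive.
- **CRP, vitamin D and PGE-M.** State that the analysis is an ANCOVA at week 12 with the week 0 value as covariate. Use the mixed model only if week 6 assays are already planned; new assays should not be required for this purpose.

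The cost is SAP wording and analysis code. No visit, sample or assay needs to be added.
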